17.5 N/A

### **18.0** Provisions to Monitor the Data to Ensure the Safety of Subjects

18.1 Site staff must first follow their own IRB's procedure for reporting and managing untoward effects.

There are three types of untoward effects to be identified: (1) those related to the participant, (2) those related to the study staff, and (3) those related to the neighborhood/community.

First, the study will catalogue any untoward effect related to the participant. Reporting is required for occurrences including social harms, psychological distress and serious life-threatening events such as suicide attempts. These may be immediately apparent to the study staff, such as the participant's emotional upset requiring referral for counseling; or they may be delayed and reported later to study staff, such as physical harm to an individual for having participated in the study. Study staff will notify the team of these untoward effects using a query system. Study staff will be briefed

during the training on the scope of possible untoward effects and instructed to report events.

Second, study staff may encounter untoward events during study visits that personally affect them. Training and guidance will seek to minimize this risk. Nonetheless, an assessment of the cost of conducting this study must include cataloguing these events as well. The protocol chairs should be notified of these events so that they may be immediately addressed, evaluated, and guidance modified or expanded to minimize similar risk to other staff.

Third, a critically important area any community-based study intends to evaluate is the impact, including untoward effects, of the project on the community. This will be done informally for this protocol with untoward events being reported to the protocol team.

All untoward effects/adverse events/unanticipated problems will also need to be reported to the FSU IRB if they meet all three of the following criteria:

"Unanticipated problems involving risks to subjects or others" (UPIRSO) refers to any incident, experience, or outcome that:

is unexpected (in terms of nature, severity, or frequency) given (a) the research procedures that are described in the protocol-related documents, such as the IRB-approved research protocol and informed consent document; and (b) the characteristics of the subject population being studied;

is related or possibly related to a subject's participation in the research; and

Suggests that the research places subjects or others at a greater risk of harm (including physical, psychological, economic, or social harm) than was previously known or recognized.

Events that meet the criteria for an UPIRSO and are also serious adverse events should be reported to the FSU IRB within one (1) week of the investigator becoming aware of the event. Any other events that meet the criteria for a UPIRSO should be reported to the IRB within two (2) weeks of the investigator becoming aware of the problem.

If the report cannot be completed in its entirety within the required time period, a preliminary report should be submitted. The report should be amended once the event is resolved and/or more information becomes available

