### 6.0 **Procedures Involved**

6.1 This study will consist of three distinct aims to develop and test the TT-C intervention for COVID vaccine hesitant AA-YA. Aims 2 and 3 procedures are premised on the formative data collected in Aim 1.

Aim 3: Conduct a hybrid type 1 effectiveness implementation 2-arm randomized controlled trial with 360 AA-YA from AL, NC, and GA.

6.2 Enrollment: After screening eligible and agreeing to be contacted, eligible responses will be reviewed individually by study staff to determine authenticity and legitimacy. In addition to eligibility criteria, staff will review bot detection values as well as location based on IP address & latitude/longitude. If determined eligible, staff complete the Verification CRF and REDCap will email the individual with a unique consent form link to complete. Once completed, REDCap will send the baseline survey linked to their unique ID in REDCap.

After the baseline survey is complete, study staff will randomize the participant with the Randomization CRF to either the intervention or control group. Based on the study arm, study staff will either email the participant with the developed SOC materials or email the participant with a unique link to create their account for the TT-C app. If SOC, the participant will be compensated at this time.

If participant is randomized to intervention arm, they will be prompted to create their account with the provided link, then will be

> directed to download and login to the TT-C app. Once account creation is confirmed in the administrator portal, study staff will compensate the participant for enrolling.

Randomization: RCT participants will be randomized via block randomization into the control condition and TT-C (remote), each with a balanced 180 participants. Assignment will be stratified by state to achieve balance between intervention and control participants within a given study state.

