Locator/Contact Information Collection: Once consented and enrolled, designated site study staff will collect contact information from the participant. Participants will be asked to provide contact information through which they can be reached. Participants will also be asked to provide valid contact information for two family members and/or friends who can be called in the event the participant cannot be reached by phone or email. Participants will be asked if messages can be left at the numbers provided. Study staff will not leave messages unless expressly permitted to do so by the participant which also will be documented. If permission is given to leave messages, site staff will assure participants that messages left with a family member or friend will only ask the participant to contact study staff and will not include any protected health information or information related to study participation.

The Contact Information Worksheet will not contain any study data and will be maintained under double locks at the study site, separate from all study records, with access limited to designated site research personnel.

Optional Monkeypox Module: Participants will also be given the opportunity to complete an optional set of questions about Monkeypox immediately following the baseline survey.

TT-C arm: Once enrolled, participants will be emailed a unique link to create their TT-C account and instructions on how to download the TT-C (remote) app from the iOS or Google Play store. They will be asked to complete the intervention within one month. Participants will be compensated for completing the baseline survey and reminded that they will be asked to return (virtually) in 1 and 3 months for follow-up.

Standard of Care arm: Research staff will provide COVID vaccine materials from the CDC to those participants in the SOC arm. Participants will be compensated for completing the baseline survey and reminded that they will be asked to complete 1 and 3-month follow-up surveys. To provide the maximum benefit through this trial, after the completion of the data collection associated with the

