### 24.0 Setting

24.1 This is a fully remote (virtual) study. Qualitative interviews will be completed via a HIPAA-compliant teleconferencing software (e.g. Zoom).

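### Section 18.1 promises to catalogue every participant harm, but no visible step in this remote trial asks all participants about harm

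*Combined protocol and SAP*

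**What the plan says.** Section 18.1 makes a broad commitment: "the study will catalogue any untoward effect related to the participant". Social harms, psychological distress and life-threatening events such as suicide attempts are all reportable. On how events come to light, it gives two descriptions. The first is of events that staff see for themselves: "These may be immediately apparent to the study staff, such as the participant's emotional upset requiring referral for counseling". The second is of events that surface only with time: "or they may be delayed and reported later to study staff". After that, "Study staff will notify the team of these untoward effects using a query system". It also opens with an instruction that "Site staff must first follow their own IRB's procedure for reporting and managing untoward effects".

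On setting, section 24.1 states: "This is a fully remote (virtual) study". Under Enrollment in section 6.2, "REDCap will send the baseline survey linked to their unique ID in REDCap". App-arm participants are "reminded that they will be asked to return (virtually) in 1 and 3 months for follow-up", and standard-of-care (SOC) participants complete surveys at the same two times. Some older wording remains: 6.4 mentions survey completion at community partner sites, and 14.2 offers counseling there.

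Section 6.4 says that data on untoward effects go onto CRFs. Section 15.1 recognises that answers or reactions may signal distress, and promises action if a participant discloses a risk of harm or harm is suspected. Section 14.2 provides a referral list by phone or e-mail to distressed participants who do not attend a partner organization.

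**The concern.** The commitment covers any harm, but both descriptions in 18.1 begin with staff seeing something or being told. In a remote trial staff have little chance to see upset while someone fills in an online survey, so the record depends largely on who chooses to speak up.

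Three things are at stake:

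- **Safety.** A participant in distress has no stated route from a survey answer to the 14.2 referral list. The IRB reporting clocks in 18.1 (one week for serious events, two weeks for others) run from when the investigator becomes aware, so an event that nobody mentions starts no clock.
- **Reading the catalogue.** A low or zero count could mean few harms or few reports.
- **Comparing arms.** Username help at onboarding and app messages with staff (15.1), and the daily website check (19.2), come with the app. Until month 3, SOC participants mainly receive materials, payment and surveys. Collection of contact details is common to both arms, but unsolicited reports may still reach staff at different rates by arm.

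**Working it through.** The plan gives no figure on this point, so the main check is textual. For each relevant provision: does it ask every participant about harm, and does it bring a worrying answer to staff?

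| Provision | What it covers | Asks all participants? | Brings an answer to staff? |
|---|---|---|---|
| 18.1 query system | Passes an event from staff to the team | No | No; starts once staff know |
| 18.1 IRB reporting | Deadlines after awareness | No | No |
| 15.1 measures and referrals | Response to disclosed or suspected harm | No | No route from a survey stated |
| 14.2 referral list | Response to distress | No | How distress is found is not stated |
| 6.4 untoward-effects CRF | Recording | Not stated; form not shown | Not stated |
| 17.1 measures | Outcomes, implementation, theory constructs, COVID risks | No harms item named; Table 5 not shown | No |
| 17.2 weekly review | Data quality | No | Not for distress |
| 19.2 daily check | Website privacy | No | Not for distress |
| Exit interviews (6.2, 17.1) | Experience, vaccine views, implementation | 12-16 in 17.1, no cap in 6.2; harm is not a stated topic | Not stated |
| Staff contact (6.2, 10.1, 15.1) | Contact details, onboarding, app messages | No | Only if noticed or volunteered |

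Response and recording are specified. The missing step is detection.

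The size of any shortfall cannot be computed. What can be shown is how much a zero count depends on being asked. Inputs from 17.1: 360 randomized and about 15% lost, so 360 x 0.85 = 306 completers, 153 per arm, as the plan states. With zero events in n people, the one-sided 95% upper limit is 1 - 0.05^(1/n).

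- If all 306 completers are asked and all say no: 1 - 0.05^(1/306) = 0.97%. Per arm: 1 - 0.05^(1/153) = 1.94%. These bound harm that completers would disclose.
- If there are no unsolicited reports among 360: 1 - 0.05^(1/360) = 0.83% bounds harm that reaches staff. If only a share c of harms reaches staff, the bound on all harm is 0.83%/c: 0.83% at c = 1, 1.7% at c = 0.5, 4.1% at c = 0.2, 8.3% at c = 0.1.

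The values of c are assumptions; the documents give none. The two bounds concern different quantities and should not be compared to measure a gain. They show only that a zero count of unsolicited reports cannot be interpreted without knowing c.

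**The case against.** The strongest reply is that the relevant files are not in view. An untoward-effects CRF exists, and its questions, timing and completer are not shown. Nor are the 1- and 3-month survey instruments, Table 5, the consent document or the IRB procedures that site staff must follow. Any of these could already hold a harms question, and then only a cross-reference is missing. This stands, and the fix allows for it.

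Second, 18.1 describes when events surface and gives examples. It does not say that detection is passive, and a later report could be a solicited one. That is fair. The point is that 18.1 does not say how its promise is met, not that it rules out asking.

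Third, other provisions help: training in adverse event reporting (6.3), a staff briefing on untoward effects (18.1), the commitment to act in 15.1, and the lead team's duty to report events and complaints (26.3). These support the handling of harms that become known; none asks everyone.

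Fourth, the stakes are low. The trial compares an educational app with CDC materials, 15.1 rates the likelihood and seriousness of emotional discomfort as minimal, and no named scale screens for distress. This limits the weight of the point.

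A reader might go further and infer that the trial never asks about harm, or that harms are being missed at some known rate. The documents support neither: the instruments are unseen, and no capture rate is given.

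**Conclusion.** The visible protocol commits to a complete record of participant harm but sets out no step that asks all participants. Distress or social harm may therefore go unrecorded, and capture may differ by arm. This rests on the visible text, on taking 24.1 at its word despite the partner-site wording in 6.4 and 14.2, and on no unseen form already asking.

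It would be wrong to infer that the efficacy results are at risk. No planned inference uses harm data, and the primary and secondary analyses are untouched. The matter is participant safety and a harms record that can be interpreted. It is worth correcting because the correction is cheap, not because a shortfall has been demonstrated.

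**What to change.** In 18.1, add an identical short harms item set to the existing 1- and 3-month surveys in both arms. Ask whether, since the last survey, the participant has had serious distress, social harm, physical harm or another problem; then ask whether they think it was related to taking part. Putting the event first avoids losing events that participants do not attribute to the study. The 4- and 6-month surveys for SOC participants who take up the app use the same forms (6.2), so the items carry over.

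Send the study coordinator a REDCap notification of any positive answer, carrying only the study ID (SID), for review within a fixed time, for example one business day. Show the 14.2 referral list at the end of every survey, including baseline. Tabulate solicited and unsolicited reports separately by arm. If the CRF or surveys already ask this, cite that form and its schedule in 18.1 instead.

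The items add to unsolicited reporting, which remains the only route between surveys and for the expected 15% (360 x 0.15 = 54) lost by month 3. They do not route answers to other questions, but they give each respondent a direct way to report distress.

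Cost, assuming one minute per survey:

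- **Participants:** 360 x 2 = 720 surveys, or 12 hours in total. If all 180 SOC participants take up the app, 720 + 180 x 2 = 1,080 surveys, or 18 hours.
- **Staff:** if 1-5% of surveys are positive (assumed), 7-36 of 720 over 9 + 3 = 12 months, or 11-54 of 1,080 over 9 + 6 = 15 months; that is about 0.6 to 3.6 a month. Because the item asks about any event, the rate could be higher; each further percentage point adds about 7 positives per 720 surveys or 11 per 1,080.
- **Set-up:** one notification rule, a short review procedure and an IRB amendment. The app does not change.

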### **19.0** Provisions to Protect the Privacy Interests of Subjects

- 19.1 All questionnaires, evaluation forms, reports, and other records will be identified by a coded number and initials only, to maintain participant confidentiality. All records with personally-identifying information will be kept in a locked, limited access area (such as a locked file cabinet). All computer entry and networking programs will be done with coded numbers and initials only. Every effort will be made to ensure that study participants are protected from risks. The main risk breach of confidentiality.
- 19.2 Participants may be concerned about the security of their data, particularly since it is collected and stored electronically. Research staff at FSU have significant experience developing security protocols for Internet-based studies, and we will take a variety of steps to ensure participant security, including using a dedicated server behind a firewall, encryption of data, separation of identifiers from responses, and password-protected access to data.

For the Tough Talks intervention arm, participants will create a unique username that does not contain any identifying information but will be their username on the app. Participants will not be able to privately communicate with each other on the app. Trained research staff at Florida Stata University will monitor the website daily to ensure violations to privacy.

19.3 N/A

### 20.0 Compensation for Research-Related Injury

20.1 N/A

20.2 N/A

20.3 N/A

### 21.0 Economic Burden to Subjects

21.1 Participants should not incur any costs for their involvement in the activities described in this protocol.

### 22.0 Consent Process

22.1 Informed consent will be obtained from participants prior to completion of any study activities. Study staff will follow HRP-090 (SOP: Informed Consent Process for Research). The informed consent process will occur online prior to completing any study procedures. Eligible participants will receive the electronic consent delivered via email. Once they have electronically signed the consent form, they will be sent the online survey hosted by REDCap.

Non-English Speaking Subjects

• N/A

#### Waiver or Alteration of Consent Process (consent will not be obtained, required information will not be disclosed, or the research involves deception)

• An online consent process for the eligibility screening is proposed. The introduction to the screening interview includes all the required elements for consent (45 CFR 46.116). No identifying information on volunteers is recorded during the online screening until a participant is determined eligible (i.e., by marking "I do consent to be screened for eligibility"). Therefore, there will be no identifying link of who agreed to be screened or not screened for the study. In addition, the screening presents minimal risk to participants and involves no procedures that would require written consent outside of a research context. Under these conditions the IRB is authorized to modify the requirements to obtain a signed consent form for some or all subjects (45 CFR 46.117 [c]).

#### Subjects who are not yet adults (infants, children, teenagers)

• N/A

#### Cognitively Impaired Adults

• N/A

### Adults Unable to Consent

N/A

# 23.0 Process to Document Consent in Writing

- 23.1 Study staff will follow HRP-091 (SOP: Written Documentation of Consent) by ensuring participants electronically sign the consent document (via REDCap eConsent).
- 23.2 N/A
- 23.3 The consent document to be completed by participants is appended to the IRB submission.

### 24.0 Setting

24.1 This is a fully remote (virtual) study. Qualitative interviews will be completed via a HIPAA-compliant teleconferencing software (e.g. Zoom).

### 25.0 Resources Available

25.1 The study team has significant experience with the conduct of internet-based recruitment and virtual/remote enrollment and completion of study activities. All staff will be adequately trained on the protocol and will practice assigned study activities before engaging with prospective or enrolled participants. Study team members will meet regularly (with the Lead PI present) to ensure proper implementation of study procedures, as outlined in the protocol. A study coordinator will be designated to coordinate all study staff, training, and activities.

#### 26.0 Multi-Site Research

- 26.1 A total of 360 participants will be enrolled in the RCT phase of this study.
- *26.2* All sites will follow the recruitment procedures outlined above. There will be no modification of materials per site.
- 26.3 The following are responsibilities of the Reviewing IRB:
  - Documenting IRB determination and provision to relying sites
  - Provision of IRB-approved materials to lead study team
  - Provision of consent form templates to relying site study teams
  - Provision of relevant IRB policies to lead study team

The following are responsibilities of the Relying IRB:

- Conflict of interest management for relying site staff
- Study team training/qualification provision to reviewing IRB
- Provision of local context information to reviewing IRB
- Incorporation of site-specific consent language

The following are responsibilities of the Lead Study Team:

- Preparation and submission of study-wide application
- Preparation and submission of site-specific application(s)
- Provision of IRB-approved documents to relying sites study teams
- Provision of consent form templates to relying site study teams
- Collection and submission of information for continuing review
- Reporting of reportable events (unanticipated problems, noncompliance, subject complaints, etc.)
- Provision of information necessary for study closure

The following are responsibilities of the Relying Study Team:

- Conflict of interest management for relying site staff
- Incorporation of site-specific consent language

26.4 N/A
